#### 13.3 Safety Criteria for Lead-In Phase and Phase 2 Portions of the Trial

Early stopping criteria based on severe toxicities and ANC engraftment failure will be used to ensure patient safety in both the safety lead-in cohort and the phase 2 portion of the trial.

The following toxic events as defined per CTCAE v5.0 will be counted separately toward the stopping rules in Table 6 and Table 7:

- Grade 4 mucositis (any site)
- Any grade 4 renal toxicity
- Any grade 4 hepatobiliary toxicity
- Grade 4 respiratory failure
- Grade 4 sepsis

#### 13.3.1 Safety Lead-in Cohort

The stopping rules for the initial safety phase are based on both the five toxic events listed above and ANC engraftment failure occurring with 30 days following transplant. The safety phase and the overall study will be stopped if either of the conditions stated for toxic events or ANC engraftment failure in Table 6 below are met. Both stopping rules are based on a one-sided exact binomial test with right-tailed significance level of  $\alpha$ =0.05 for sample sizes 4 to 14. For the toxic events the assumed null proportion is 0.30 for each of the five toxicities listed above, while for ANC engraftment failure the assumed null proportion of 0.10.

After enrollment to the safety lead-in cohort has been completed, accrual to the study will be temporarily suspended until all patients have completed toxicity and engraftment assessments through 30 days post-transplant. These assessments will be reviewed by study monitors and the Data and Safety Monitoring Committee (DSMC, Section 14.2). If the DSMC concludes that the reported toxicities and engraftment meet safety criteria to continue, the study will reopen to accrual.

Accrued Sample Size	ANC Engraftment Failure Stopping Rule	Toxic Event Stopping Rule
4,5	2	3
6,7	2	4
8	2	5
9-10	3	5
11,12	3	6
13,14	3	7

 Table 6. Number of Observed ANC Engraftment Failures and Toxic

 Events (Measured Separately for Each Toxicity Outcome) Needed to

 Stop Trial During Safety Lead-In Given Accrued Sample Size

#### 13.3.2 Stopping Criteria for Phase 2 portion

If criteria are met to proceed to the phase 2 portion of the trial, the rates of engraftment failures and severe toxicities will continue to be monitored, and the early stopping rules outlined in Table 7 and Table 8 will be employed.

The stopping rules for the phase 2 portion of the study are based on an exact binomial test using the null proportion of 0.30 for each of the five toxicities listed above and a one-sided, right-tailed significance level of  $\alpha$ =0.05 for sample sizes 2 to 55 (Table 7).

ANC engraftment failure will also be used for a stopping rule based on an exact binomial test using the null proportion of 0.10 for engraftment failure and a one-sided right-tailed significance level of  $\alpha$ =0.05 for sample sizes 4 to 55 (Table 8). ANC engraftment failure is defined as failure to achieve hematopoietic engraftment (Section 10.1) within 30 days after transplant.

Accrued Sample Size	Stopping Rule
15-17	8
18-20	9
21-22	10
23-25	11
26-28	12
29,30	13
31-33	14
34-36	15
37-39	16
40,41	17
42-44	18
45-47	19
48-50	20
51-53	21
54,55	22

 Table 7. Number of Observed Toxic Events (Measured Separately for Each Toxicity

 Outcome) Needed to Stop Phase 2 Portion of Trial Given Accrued Sample Size

 Table 8. Number of Observed ANC Engraftment Failures Needed to Stop Phase 2

 Portion of Trial Given Accrued Sample Size

Accrued Sample Size	Stopping Rule
15-20	4
21-27	5
28-34	6
35-41	7
42-48	8
49-55	9

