# **10 MEASUREMENT OF EFFECT**

# 10.1 Engraftment

Hematopoietic engraftment is defined as both of the following:

- Recovery from post-transplant cytopenia with an absolute neutrophil count of ≥ 0.5 x 10^9 /L for 3 consecutive measurements or ≥ 1.0 x 10^9 /L for 1 day; and
- Platelet count of  $\ge 20 \times 10^9$  /L for 7 days without transfusion.

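### The stopping rule named for ANC engraftment failure is defined by a two-part event that also requires platelet recovery, and the plan does not say which event its 0.10 null describes

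*Combined protocol and SAP*

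**What the plan says.** Section 13.3 opens with "Early stopping criteria based on severe toxicities and ANC engraftment failure will be used to ensure patient safety". For the lead-in, Section 13.3.1 bases one of its two rules on "ANC engraftment failure occurring with 30 days following transplant" and gives the null as "for ANC engraftment failure the assumed null proportion of 0.10". It makes the rule mandatory: "The safety phase and the overall study will be stopped if either of the conditions stated" in Table 6 are met. It does not define the event.

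Section 13.3.2 carries the rule into phase 2. The Table 8 caption begins "Number of Observed ANC Engraftment Failures Needed to Stop Phase 2". The sentence stating the test has ANC engraftment failure as its subject, but sets the test up "using the null proportion of 0.10 for engraftment failure", without the qualifier. The definition follows: "ANC engraftment failure is defined as failure to achieve hematopoietic engraftment", by reference to Section 10.1, within 30 days of transplant.

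Section 10.1 has a two-part criterion: "Hematopoietic engraftment is defined as both of the following". The first part is neutrophil recovery (at least 0.5 x 10^9/L on three consecutive measurements, or at least 1.0 x 10^9/L on one day). The second is a platelet count of at least 20 x 10^9/L sustained over seven transfusion-free days.

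**The concern.** The name of the event points to neutrophils only, while the definition brings in platelets. Consider a patient whose neutrophils have recovered by Day 30 but whose platelets have not met the second part. By the definition that patient is a failure; by the name, not. The count feeds a rule that closes the study, so it should be clear before any count is seen which patients contribute.

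The null has the same problem. The thresholds are meant to flag a failure rate above 0.10. If 0.10 was chosen for neutrophil failure alone, applying it to the two-part event would stop the trial more readily than intended. If it was chosen for the two-part event, the rule is coherent and only its name is wrong. The documents do not say which.

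**Working it through.** **1. The sections side by side**

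| Element | Section 13.3.1 (lead-in) | Section 13.3.2 (phase 2) |
|---|---|---|
| Name of event | ANC engraftment failure | ANC engraftment failure |
| Definition | none | failure of the two-part criterion in Section 10.1 |
| Window | 30 days | 30 days |
| Event tied to the 0.10 null | ANC engraftment failure | engraftment failure, in a sentence whose subject is ANC engraftment failure |

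No neutrophil-only definition of failure appears anywhere. Using the Section 13.3.2 definition in the lead-in is an inference from the shared name, window and null.

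**2. The plan's own counts**

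The stated test is exact binomial, one-sided, null 0.10, alpha 0.05. The boundary should be the smallest r with P(X >= r | n, 0.10) <= 0.05.

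- n = 14: P(X >= 3) = 0.158, P(X >= 4) = 0.044. Printed 3.
- n = 31: P(X >= 6) = 0.083, P(X >= 7) = 0.031. Printed 6.
- n = 55: P(X >= 9) = 0.094, P(X >= 10) = 0.044. Printed 9.

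The printed counts are one below the stated test at every n from 4 to 55. That is a separate matter. The printed counts are used below because they are the rule as written.

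**3. Direction of the mismatch (no assumed rate)**

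Let A be the number of patients without neutrophil recovery by Day 30, and B the number with neutrophil recovery but no qualifying platelet recovery. The two-part count is C = A + B, so C >= A always. With A = 0, C = B, and platelet-only failures alone reach the printed count at:

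| Patients accrued | Platelet-only failures that stop the trial |
|---|---|
| 4-8 | 2 |
| 9-14 | 3 |
| 15-20 | 4 |
| 21-27 | 5 |
| 28-34 | 6 |
| 35-41 | 7 |
| 42-48 | 8 |
| 49-55 | 9 |

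**4. How often the two readings could differ (illustration only)**

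The documents give no neutrophil, platelet-only or two-part failure rate, and no schedule of looks for this rule. All of these are assumptions, as is independence between patients.

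Let f_n(k) be the probability of k events among n patients with no stop so far, at event rate p. Then f_n(k) = f_{n-1}(k)(1 - p) + f_{n-1}(k - 1)p. At each look, the mass with k at or above the printed count moves to S(p), the probability of having stopped.

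| Assumed event rate p | S(p) by n = 55, look after every patient from n = 4 | S(p) by n = 55, looks at 14, 31 and 55 |
|---|---|---|
| 5% | 7.57% | 3.22% |
| 10% | 33.13% | 22.24% |
| 15% | 67.64% | 57.77% |
| 20% | 90.05% | 85.77% |

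Because C >= A, every trial that stops on the neutrophil count also stops on the two-part count, and no later. The probability that one reading stops and the other does not is therefore S(a + b) - S(a), where a is the neutrophil rate and b the platelet-only rate.

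- a = 5%, b = 5%: 33.13 - 7.57 = 25.6% (every patient); 22.24 - 3.22 = 19.0% (three looks).
- a = 10%, b = 5%: 67.64 - 33.13 = 34.5% (every patient); 57.77 - 22.24 = 35.5% (three looks).
- b = 0: 0% under either schedule.

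A joint simulation of both counts (200,000 trials per setting) agreed to within 0.1 percentage point and produced no case in the reverse direction. With the boundaries one higher that the stated alpha implies, the same differences are 11.9% and 8.0% for 5% plus 5%, and 32.1% and 29.0% for 10% plus 5%.

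**The case against.** The strongest reply is that an express definition with a cross-reference outranks a short label. Section 13.3.2 says what the event is, and the rule can be applied as written. Nearby wording fits that reading: the null in Section 13.3.2 is attached to engraftment failure without the qualifier, and Section 13.3.1 has the DSMC review engraftment in general terms. This stands. A reader might infer that the plan leaves two equally available rules with nothing to choose between them; the text does not support that, because following the label means setting the defining sentence aside.

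The reply does not remove the point. The definition appears only in the phase 2 subsection, whereas the explicit statement that the study will be stopped is in the lead-in subsection, which has none. Even if the definition governs throughout, the basis of the 0.10 null stays open.

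It can also be said that the mismatch is protective, since the two-part count can only stop the trial sooner and misses no neutrophil failure, and that both blood counts are routine, so the DSMC can tell the two kinds of failure apart. Both are true. The exposure is an unneeded stop, and a DSMC asked whether engraftment meets the safety criteria still needs to know what the criterion is.

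Finally, the probabilities rest on rates and looks that the documents do not give. That is correct, and they show only that the choice of event can matter.

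**Conclusion.** The point holds as a mismatch between name and definition, together with an unstated basis for the null. Read literally, the definition selects the two-part event in phase 2, and by inference in the lead-in, so a patient with full neutrophil recovery can count as an ANC failure. That much is textual and rests on no assumption. So does the direction: the definition can stop a trial that the label would continue, never the reverse, with as few as 2 platelet-only failures among the first 4-8 patients.

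The practical size is not fixed by the documents. It runs from 0% with no platelet-only failures to about a third of trials at an assumed 10% plus 5%. A reader might infer that the rule is known to over-stop, or that 0.10 is wrong for the event as defined. Neither is supported: no failure rate is given, and 0.10 may have been meant for the two-part event. The NRM test and its decision thresholds are unaffected. The point should be fixed because the rule ends the study and the correction is cheap.

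**What to change.** Reconcile Sections 10.1, 13.3.1 and 13.3.2 so that the label, the definition and the 0.10 null describe one event, stated for both the lead-in and phase 2. The choice of event is the sponsor's.

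- **If the neutrophil event is meant:** refer the rule and Tables 6 and 8 to the neutrophil part of Section 10.1 only, and leave Section 10.1 unchanged for the secondary endpoint of time to engraftment. Downside: platelet non-recovery no longer counts toward stopping, although Section 1.2 links the agent to both engraftment time and transfusion need.
- **If the two-part event is meant:** rename the rule in Section 13.3 and both captions, and confirm that 0.10 is the null for that event or re-derive the thresholds. Downside: a stop may reflect platelets alone.

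The cost is a short wording amendment, plus new thresholds only if the two-part event is chosen with a different null. No new data are needed: blood counts are routine, and Table 5 footnote G already provides for collecting laboratory values that bear on endpoints or stopping criteria.

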# **14 DATA AND SAFETY MONITORING**

## 14.1 Study Team

The study team minimally consists of the sponsor-investigator, the co-investigators, the study coordinator, the clinical research associate, and the study biostatistician. While patients are on treatment, the sponsor-investigator and the study coordinator will meet at least monthly and will meet at least quarterly with the study biostatistician to review study status. This review will include, but not be limited to, reportable AEs and UPs and an update of the ongoing study summary that describes study progress in terms of the study schema. All meetings including attendance are documented.

#### 14.2 Monitoring and Auditing

14.2.1 MCC Compliance Office

Compliance specialists in the MCC Compliance Office will provide ongoing monitoring and auditing for this study.

14.2.2 Data and Safety Monitoring Committee (DSMC)

The study will be reviewed by the MCC DSMC initially according to the risk level specified by the MCC Protocol Review and Monitoring Committee (PRMC) and then according to a schedule based on study status and quality indicators. The DSMC will review reports provided by the sponsor-investigator/study team and the MCC Compliance Office focusing on data integrity and patient safety.

# **15 REGULATORY COMPLIANCE AND ETHICS**

## 15.1 Ethical Standard

This study will be conducted in conformance with the principles set forth in *The Belmont Report: Ethical Principles and Guidelines for the Protection of Human Subjects of Research* (US National Commission for the Protection of Human Subjects of Biomedical and Behavioral Research, April 18, 1979).

## 15.2 Regulatory Compliance

This study will be conducted in compliance with:

- The protocol
- Federal regulations, as applicable, including: 21 CFR 50 (Protection of Human Subjects/Informed Consent); 21 CFR 56 (Institutional Review Boards); 21 CFR 312 (IND Application); and 45 CFR 46 Subparts A (Common Rule), B (Pregnant Women, Human Fetuses and Neonates), C (Prisoners), and D (Children)

#### 15.3 Institutional Review Board

The VCU IRB, which is registered with the Office for Human Research Protections, will review and provide approval for the protocol, the associated informed consent document, material that will be provided to participating patients, and any recruitment material. Any amendments to the protocol, consent form, or other materials will also be approved by the IRB.

#### 15.4 Informed Consent Process

Informed consent is a process that is initiated prior to the individual's agreeing to participate in the study and continues throughout the individual's study participation. Discussion of risks and possible benefits of this therapy will be provided to the patients and their families. IRB-approved consent forms describing the study interventions, study procedures, and risks are given to the patient and written documentation of informed consent is required prior to starting intervention/administering study product.

The patient will be asked to read and review the document. Upon reviewing the document, the investigator will explain the research study to the patient and answer any questions that may arise. The patient will sign the informed consent document prior to any procedures being done specifically for the study. The patients should have the opportunity to discuss the study with their surrogates or think about it prior to agreeing to participate. Patients may withdraw consent at any time throughout the course of the trial. A copy of the informed consent document will be given to patients for their records. The rights and welfare of the patients will be protected by emphasizing to them that the quality of their medical care will not be adversely affected if they decline to participate in this study.

#### 15.5 Patient Confidentiality and Access to Source Documents/Data

Patient confidentiality is strictly held in trust by the participating investigators and their staff. This confidentiality includes the clinical information relating to participating patients, as well as any genetic or biological testing.

The study protocol, documentation, data, and all other information generated will be held in strict confidence. No information concerning the study or the data will be released to any unauthorized third party without prior written approval of the sponsor-investigator.

The sponsor-investigator will allow access to all source data and documents for the purposes of monitoring, audits, IRB review, and regulatory inspections.

The study monitor or other authorized representatives of the sponsor-investigator may inspect all documents and records required to be maintained by the investigator, including but not limited to, medical records (office, clinic, or hospital) and pharmacy records for the patients in this study. The clinical study site will permit access to such records.

# 16 DATA HANDLING AND RECORD KEEPING

#### 16.1 Data Management Responsibilities

The sponsor-investigator is responsible for: (i) the overall conduct of the investigation; (ii) ongoing review of trial data including all safety reports; and (iii) apprising participating investigators of any UPs. Participating investigators are responsible for reporting SAEs and UPs as required in Section 8.

Any laboratory conducting correlative studies must maintain the laboratory records and documentation (laboratory notebooks, laboratory protocols, print-outs, recordings, photographs, etc).

#### **16.2 Source Documents**

Source documents for clinical information (patient history, diagnosis, clinical and diagnostic test reports, etc) are maintained in the patient's clinical file. Source documents for the correlative studies are maintained in the laboratory conducting the study.

## 16.3 Case Report Forms and Data Collection

MCC OnCore data management will provide standard and study-specific electronic case report forms (eCRFs) to capture all the information required by the protocol. The eCRFs will be approved by the study team to ensure the most effective data acquisition.

The investigator(s) and study coordinator(s) must maintain source documents for each patient in the study. All information on the eCRFs will be traceable to the source documents, which are generally maintained in the patient's file.

All eCRFs should be completed and available for collection within a timely manner, preferably no more than 14 days after the patient's visit.

## 16.4 Study Record Retention

As applicable, study records will be maintained a minimum of 6 years beyond: (i) the publication of any abstract or manuscript reporting the results of the protocol; (2) the submission of any sponsored research final report; or (iii) submission of a final report to clinicaltrials.gov.

